# Table 2.Estimated Cumulative Number of Ritlecitinib-Exposed Patients by
Accrual Year

Table 3 shows the background age-standardized IRs (number of patients with events per 1,000 person-years (PYs)) of selected safety events of interest in patients with AA obtained from the population-based electronic healthcare registers in Denmark (Pfizer data on file). Number of PYs needed to observe approximately 1 event, given the estimated background rates and a doubling of the background rates is also presented.

PFIZER CONFIDENTIAL

CT24-WI-GL02-RF02 5.0 Non-Interventional Study Protocol Template For Secondary Data Collection Study 01-Aug-2023 Page 27 of 47

# Table 3.Age Standardized Incidence Rates (IRs) of Selected Safety Events of
Interest in Patients with Alopecia Areata (AA) in Denmark (Pfizer
data on file)

Event	IR per 1,000 PYs	PYs Needed to Observe Approximately 1 Event, Given Background IR	PYs Needed to Observe Approximately 1 Event, Given Doubling of Background IR
Any primary malignancy excluding NMSC a	1.13	885	442
Thromboembolic events	1.17	855	427
DVT	0.87	1,149	575
PE	1.09	917	459
ATE	2.50	400	200
MACE b	1.41	709	355
Herpes zoster infection	1.83	546	273
Serious infections c,d	1.89	529	265

a. Incidence rate of malignancy including NMSC in patients with AA not available.

b. Defined by the following outcomes: CV death; acute myocardial infarction; unstable angina; ischemic stroke; haemorrhagic stroke; hospitalization due to heart failure; coronary revascularization by percutaneous intervention or coronary artery bypass graft.

c. Including the following infection types: abscess, bacteraemia, candidiasis and other fungal infections, coronavirus disease of 2019 (COVID-19), female pelvic infections, heart infections (acute rheumatic fever, infectious peri- or myocarditis, endocarditis), human immunodeficiency virus disease, infections of central nervous system, infectious complications of procedures, catheters etc., influenza, intra-abdominal infections, male genital infection, miscellaneous bacterial infection, miscellaneous viral infections, obstetrical infections, other lower-respiratory tract infections, parasitic infections, pneumonia, sepsis, sexually transmitted diseases, skin infections, and viral hepatitis. d. Incidence rate of opportunistic infections in patients with AA not available.

Abbreviations: AA = alopecia areata; ATE = arterial thromboembolism; CV = cardiovascular; DVT = deep vein thrombosis; IR = incidence rate; NMSC = nonmelanoma skin cancer; MACE = major adverse cardiovascular event; PE = pulmonary embolism; PY(s) = person-year(s)

With an estimated 835 ritlecitinib-exposed patients accrued over 8 years (Table 2), and with a 10-year study period, the expected number of observed PYs will be 0\*9 + 74\*8 + 96\*7 + 110\*6 + 127\*5 + 144\*4 + 161\*3 + 123\*2 = 3,864, assuming no lost to follow-up. A 1:1 ratio of ritlecitinib:comparator patients would yield a total of 7,728 PYs and an expected number of events of 9, 10, and 15 for the endpoints malignancy, thromboembolic events, and serious infections during follow-up. In this setting, there would be sufficient power to detect a minimum HR of 6.7, 6.4, and 4.3 for the endpoints malignancy, thromboembolic events, and serious infections (or other outcomes of similar incidence). However, the analysis will be conducted separately by data source and each individual data source is unlikely to accrue 835 ritlecitinib-exposed patients.

Minimum detectable HRs will be lower for the subgroup analysis of patients with a minimum of 5 years of follow-up (during the 10-year study period). 407 ritlecitinib-exposed patients

PFIZER CONFIDENTIAL

CT24-WI-GL02-RF02 5.0 Non-Interventional Study Protocol Template For Secondary Data Collection Study 01-Aug-2023 Page 28 of 47 accrued over 5 years (Table 2), assuming a 1:1 ratio and no lost to follow-up, would provide sufficient power to detect minimum HRs of 10.3, 9.9, and 6.1 for the endpoints malignancy, thromboembolic events, and serious infections.

Of note, it is possible that the comparator groups may be larger than the ritlecitinib group, given baricitinib's earlier approval date and the potential inclusion of other EU approved systemic treatments. If patients are receiving baricitinib at a substantially higher rate than ritlecitinib (e.g., a ratio of 2:1 or greater), then the minimum detectable hazard ratios could be met with fewer ritlecitinib-exposed patients.

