The Swedish Medical Products Agency's guideline on medical treatment of AA, last modified on 06 February 2024, currently cites absence of an effective treatment for AA, however, the guideline is pending an update in early 2024 (18). In France, as of 25 October 2023, baricitinib is the first-line treatment for severe adult alopecia (scalp involvement  $\geq$  50%), with the importance of monitoring various biological parameters (including haematological and lipid levels) and the contraindication in pregnancy. In accordance with the conclusions of the Pharmacovigilance Risk Assessment Committee (PRAC), patients ages 65 years and older, patients with a history of atherosclerotic cardiovascular disease or other cardiovascular risk factors (long-term or former smokers), and patients with risk factors for malignant tumours are advised that baricitinib should only be used in the absence of appropriate therapeutic alternatives. The benefit/risk balance of treatment should be reassessed at regular intervals. Discontinuation of treatment should be considered in patients who show no therapeutic benefit after 36 weeks of treatment (19).

Safety surveillance studies using electronic healthcare databases have been used to successfully monitor real-world safety of newly approved products across a wide spectrum of therapeutic areas and safety events. As part of the ritlecitinib pharmacovigilance plan, this non-interventional study (NIS) based on routinely collected electronic healthcare data from routine clinical practice will be conducted to actively monitor the safety events of interest following exposure to ritlecitinib, baricitinib or other approved systemic treatments for AA following the EU approval of ritlecitinib.

This NIS is designated as a post-authorization safety study (PASS) and is a commitment to the EMA.

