# 9.1.2. Index Date and Follow-Up

The index date will be the date of the eligible initiation of ritlecitinib, baricitinib or another approved systemic treatment for AA during the cohort accrual period, as recorded in the data sources. Follow-up will start on the date after the index date and continue until the earliest of disenrollment from the data source, an event of interest, or censoring.

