### Figure 1. Study Design Schema

```
Cohort accrual period [15 September 2023 – 14 September 2031]
(First dispensing of ritlecitinib, baricitinib or another approved systemic AA treatment)
Day 0 = index date in a given exposure cohort
```

Diagnosis of Alopecia areata [-5 years, 0 days]	
Exclusion: age <12 years on index date [0, 0]	
Exclusion: minimal residence [-365 days, -1 day]	
Washout period to define new users [-5 years, -1 day]	
	Follow up Window Days (1, Censor a ]

a. Earliest of: outcome of interest, or censoring by discontinuation/switch, death, disenrollment, end of the study period on 15 September 2033.

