### 9.5. Study Size

All ritlecitinib-treated patients meeting study inclusion and exclusion criteria in all data sources during the accrual period will be included in the study. Estimated anticipated group size of the ritlecitinib-exposed population across the three databases is provided in Table 2. Overall, an estimated 835 ritlecitinib-exposed patients are expected to be accrued over 8 years. Of note, these sample size calculations are estimates based on the projected uptake of ritlecitinib in the study countries and are subject to the actual uptake and final study inclusion and exclusion criteria.

			Y	ears Post-	-Approval			
	Year 1	Year 2	Year 3	Year 4	Year 5	Year 6	Year 7	Year 8
Estimated New Patients Treated Per Year in Denmark, France, and Sweden (based on projected market uptake)	0	148	192	220	255	288	321	247
Estimated 50% Meeting Eligibility Criteria (conservative estimate, true proportion may be higher)	0	74	96	110	127	144	161	123
Estimated Cumulative Number of Patients Exposed to Ritlecitinib	0	74	170	280	407	551	712	835

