# 9.7.5. Sensitivity Analyses

A number of sensitivity analyses will be performed as listed below. Each sensitivity analysis will aim to examine the robustness of the findings given certain assumptions about the analysis. Each sensitivity analysis will be performed on the entire study population and, with the exception of the analysis parameter that is being altered, will use all main analysis procedures:

- Re-estimating the IRs and HRs with shorter grace periods for defining treatment discontinuation/switch: e.g., zero days and 30 days
- Re-estimating the IRs and HRs for acute-onset events using an intention-to-treat (ITT)-like approach, whereby follow-up will not be censored by treatment discontinuation
- Re-estimating the IRs and HRs for malignancy excluding NMSC and NMSC, using 6 months instead of 12 months after treatment initiation as the minimum induction period
- Re-estimating the IRs and HRs among patients without a record of rheumatoid arthritis, atopic dermatitis, or juvenile idiopathic arthritis on or before index date
- Re-estimating the IRs and HRs for MACE using an alternative definition

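### Section 9.5 sizes the study on uncensored person-time with no induction period, so its expected events and minimum hazard ratios are more favourable than the planned main analyses support

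*Protocol*

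**What the plan says.** **Sizing (9.5).** "Overall, an estimated 835 ritlecitinib-exposed patients are expected to be accrued over 8 years". Each yearly group is multiplied by all the calendar years left, from 8 down to 2, which gives "3,864, assuming no lost to follow-up". Then "A 1:1 ratio of ritlecitinib:comparator patients would yield a total of 7,728 PYs", from which the events and minimum HRs follow. A second set of HRs (10.3, 9.9 and 6.1) is given for the 407 patients accrued in the first five years. Section 9.2 describes loss to follow-up as small and mainly due to emigration.

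**Censoring.** The footnote to Figure 1 ends follow-up at the "Earliest of: outcome of interest, or censoring by discontinuation/switch, death, disenrollment" or the end of the study period. Section 9.3.1 lets exposure run for 90 days after estimated discontinuation. Section 9.7.2 classes thromboembolic events and all infection endpoints as acute-onset. Section 9.7.5 then lists, as a sensitivity analysis for acute-onset events, re-estimation "using an intention-to-treat (ITT)-like approach, whereby follow-up will not be censored by treatment discontinuation". Section 9.7.2 also says that approaches with and without censoring will be considered.

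**Induction.** Section 9.7.5 includes a malignancy sensitivity analysis "using 6 months instead of 12 months after treatment initiation as the minimum induction period", so 12 months is the main-analysis value. Section 9.7.2 says that events in a prespecified period after index may be disregarded and treated as prevalent. Section 9.1.2 gives one general rule: "Follow-up will start on the date after the index date".

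**The concern.** The only caveat on the 3,864 person-years is loss to follow-up. In this protocol that means leaving the data source, not stopping treatment. Yet the main analysis of two of the three sized endpoints stops counting time soon after treatment stops, and the main analysis of the third disregards events in the first year. Section 9.5 mentions neither rule.

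The protocol's background section shows that some stopping is to be expected. For baricitinib in France it reports that "Discontinuation of treatment should be considered in patients who show no therapeutic benefit after 36 weeks of treatment". That concerns the comparator and gives no rate, but it makes full persistence to 2033 an unlikely base case.

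At stake is what the study can be said to detect. In a safety study, overstated person-time makes an absence of signal look more informative than it is. The same person-years also govern the precision of the primary incidence rates.

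**Working it through.** **Inputs.**
- Eligible accrual by year (Table 2): 0, 74, 96, 110, 127, 144, 161, 123; sum 835.
- Year weights (9.5): 9, 8, 7, 6, 5, 4, 3, 2.
- Background rates per 1,000 person-years (Table 3): malignancy excluding NMSC 1.13; thromboembolic events 1.17; serious infections 1.89.
- Significance level, power and formula: not stated. Schoenfeld's formula at 1:1, two-sided 5% and 80% power was inferred because it reproduces the stated HRs: minimum HR = exp(2 × (1.960 + 0.842) / √events) = exp(5.603 / √events).

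**Step 1: reproduce 9.5.** 74×8 + 96×7 + 110×6 + 127×5 + 144×4 + 161×3 + 123×2 = 3,864; doubled, 7,728.

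| Endpoint | Events = 7,728 × rate / 1,000 | Stated | HR | Stated |
|---|---|---|---|---|
| Malignancy | 8.73 | 9 | 6.66 | 6.7 |
| Thromboembolic | 9.04 | 10 | 6.45 | 6.4 |
| Serious infection | 14.61 | 15 | 4.33 | 4.3 |

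The stated events are these values rounded up. For the 5-year subset, 74×8 + 96×7 + 110×6 + 127×5 = 2,559 person-years per cohort, giving HRs of 10.3, 9.9 and 6.1, as stated.

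**Step 2: malignancy with the 12-month induction period.** Each patient loses one year.
- Overall: 3,864 − 835 = 3,029 per cohort. Events = 2 × 3,029 × 1.13 / 1,000 = 6.8. HR = exp(5.603 / √6.85) = 8.5. Power at HR 6.7 falls from 80% to 70%.
- 5-year subset: 2,559 − 407 = 2,152. Events = 4.9. HR = 12.7, against 10.3 stated.

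**Step 3: allow for mid-year accrual.** The year weights credit patients only from the end of their accrual year. Adding half a year each gives 3,864 + 417.5 = 4,281.5.
- Overall malignancy: 4,281.5 − 835 = 3,446.5; 7.8 events; HR 7.4.
- 5-year subset: 2,559 + 203.5 − 407 = 2,355.5; 5.3 events; HR 11.3.

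**Step 4: acute endpoints, illustration only.** The documents give no stopping rate. Assume that a constant proportion q stops per year, equally in both cohorts, so the hazard is h = −ln(1 − q), with a grace period of 0.25 year. Expected on-treatment time for a patient with T years left is 0.25 + (1 − exp(−h(T − 0.25))) / h. For example, with q = 10% and T = 8 this is 5.55 years instead of 8. Summed over accrual with the protocol's year weights:

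| Assumed q | Person-years per cohort | Thromboembolic: events, HR | Serious infection: events, HR |
|---|---|---|---|
| 10% | 3,040 | 7.1, 8.2 | 11.5, 5.2 |
| 20% | 2,420 | 5.7, 10.5 | 9.1, 6.4 |
| 30% | 1,947 | 4.6, 13.8 | 7.4, 7.9 |

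With mid-year accrual, on-treatment time drops below 3,864 once stopping exceeds about 3.9% per year.

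**The case against.** The strongest reply is that little depends on these numbers. All eligible patients are included whatever the calculation shows. The primary objective is to estimate incidence rates. The HRs concern an exploratory comparison, made only if study size permits and only in the final report, under a decision rule left to the SAP. Section 9.5 already warns that single data sources are unlikely to reach 835 patients. All of this stands and limits the weight of the point. None of it tells the reader that censoring and induction were left out.

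Three stronger readings are tempting, and the documents do not support them.

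- *The malignancy rate will be about 22% too low.* First-year time is 835 / 3,864 = 22% of the total, and Section 9.1.2 starts follow-up the day after index for all outcomes. The bias would arise only if that rule were applied literally to malignancy. Section 9.7.2 points the other way: it treats index date and follow-up separately for delayed outcomes and excludes patients with prevalent conditions.
- *The stated figures match no planned analysis.* For the two acute endpoints, 3,864 person-years fits the planned uncensored sensitivity analysis, and Section 9.7.2 keeps both censoring approaches open.
- *The arithmetic is wrong.* The person-years and all six HRs reproduce. The fault lies in which person-time is counted.

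It is also fair to object that the acute-endpoint figures rest on assumed stopping rates. Only their direction follows from the protocol.

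**Conclusion.** The point holds as a misstated sizing figure. Section 9.5 presents as expected a person-time total that applies neither the on-treatment censoring nor the 12-month induction period implied for the main analyses.

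For malignancy the correction needs only the protocol's figures and the inferred formula: 6.8 events and HR 8.5 in place of 9 and 6.7, or 7.8 and 7.4 if mid-year accrual is credited. In the 5-year subset the HR is 12.7, or 11.3 with mid-year accrual, in place of 10.3. This does not require settling whether malignancy is also censored at discontinuation, which the protocol leaves unclear.

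For thromboembolic events and serious infections the stated figures are an upper bound on what the main analysis can offer under the protocol's year weights. The gap cannot be computed from the document. At an assumed 10% to 30% stopping per year, the minimum HRs would be about 8 to 14 and 5 to 8.

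The broad message of 9.5, that only large relative effects are detectable, is unchanged and becomes somewhat more pronounced.

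**What to change.** In Section 9.5:
1. Label 3,864 person-years, with its events and HRs, as the uncensored figure without an induction period.
2. Restate malignancy, overall and for the 5-year subset, with the 12-month induction period, and say whether accrual is credited from mid-year or year end.
3. Give person-years, events and minimum HRs for thromboembolic events and serious infections over a stated range of persistence, including the 90-day grace period.
4. State the formula, significance level and power.

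As a clarification, align Section 9.1.2 with 9.7.2 by saying that malignancy person-time starts at the end of the induction period (12 months; 6 in the sensitivity analysis), among patients still followed and free of the event.

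The cost is a rewritten paragraph and one added sentence. The stated figures become less favourable. No extra patients or data are needed.

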# 8.2. Primary Objective

The primary objective is to estimate the IRs of safety events of interest among patients with AA initiating ritlecitinib and patients with AA initiating baricitinib or other approved systemic treatments for AA in a real-world setting. The following are the primary safety events of interest:

- Thromboembolic events (including VTE and arterial thrombosis)
- Herpes zoster (HZ)
- Serious infections
- Opportunistic infections
- Malignancy
  - Malignancy excluding nonmelanoma skin cancer (NMSC)
  - o NMSC
- Major cardiovascular event (MACE)
- Neurological events of interest
  - Peripheral neuropathy
  - Sensorineural hearing loss
  - o Migraine
  - o Seizures and seizure disorders
  - o Demyelinating disorders including multiple sclerosis
  - o Neurodegenerative disorders
- Bone fractures
- Growth metrics in adolescents (height and weight, conditional on sufficient data available beyond age 12 years; Denmark only)

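### The expected events and minimum HRs for thromboembolic events in Section 9.5 rest on a Table 3 rate (1.17 per 1,000 PY) that conflicts with the table's own ATE rate (2.50)

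*Protocol*

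**What the plan says.** Section 8.2 lists the endpoint as "Thromboembolic events (including VTE and arterial thrombosis". Section 9.3.2 repeats this and states that arterial thrombosis includes MI and stroke. The Table 1 row for the endpoint also names arterial thrombosis beside DVT and PE.

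Table 3 gives age-standardized background rates per 1,000 PY in Danish patients with AA, followed by the PYs needed for one event at the background rate and at twice that rate:
- composite: "Thromboembolic events 1.17 855 427"
- deep vein thrombosis: "DVT 0.87 1,149 575"
- pulmonary embolism: "PE 1.09 917 459"
- arterial thromboembolism: "ATE 2.50 400 200"
- MACE: 1.41, with footnote b listing acute MI, ischaemic and haemorrhagic stroke, unstable angina, heart failure hospitalization, revascularization and CV death.

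MACE and serious infections have footnotes that define them. The thromboembolic and ATE rows have none.

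The text after Table 3 puts ritlecitinib follow-up at "3,864, assuming no lost to follow-up". It continues: "A 1:1 ratio of ritlecitinib:comparator patients would yield a total of 7,728 PYs", with "an expected number of events of 9, 10, and 15 for the endpoints malignancy, thromboembolic events, and serious infections during follow-up". The minimum HRs for malignancy, thromboembolic events and serious infections are 6.7, 6.4 and 4.3, or 10.3, 9.9 and 6.1 in patients accrued in the first five years.

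**The concern.** A composite counted at first occurrence should not run at less than half the rate of one of its own components in the same population. Table 3 shows exactly that: 1.17 for the composite against 2.50 for ATE. Section 9.5 then carries the 1.17 forward as the rate of the full endpoint.

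At stake are the planning figures for a listed primary safety event: 855 and 427 PYs per event, 10 expected events, and minimum HRs of 6.4 and 9.9. Section 9.5 also extends its HRs to other outcomes of similar incidence. A reader would conclude that only a more than six-fold hazard is detectable for thromboembolism, although the protocol's own ATE rate implies something quite different.

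**Working it through.** **Inputs.** Total PY 7,728 (Section 9.5). PY in the 5-year subset, from the accrual terms in Section 9.5: 74×8 + 96×7 + 110×6 + 127×5 = 2,559 per group, so 5,118 at 1:1. Rates are from Table 3. Alpha and power are not stated; two-sided 5% and 80% are assumed.

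**Formulas.** Expected events d = PY × rate / 1,000. Minimum HR = exp(2 × (1.960 + 0.842) / √d), which is Schoenfeld's formula inverted for 1:1 groups.

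**Step 1: reproduce the printed figures.**

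| Endpoint | Rate | d, all | HR, all (printed) | d, subset | HR, subset (printed) |
|---|---|---|---|---|---|
| Malignancy | 1.13 | 8.73 | 6.66 (6.7) | 5.78 | 10.28 (10.3) |
| Thromboembolic | 1.17 | 9.04 | 6.45 (6.4) | 5.99 | 9.87 (9.9) |
| Serious infections | 1.89 | 14.61 | 4.33 (4.3) | 9.67 | 6.06 (6.1) |

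All six HRs are recovered to within rounding. One-sided 5% (5.23 for thromboembolic events) and 90% power (8.64) do not fit. So 1.17 is the rate used, and the arithmetic that follows from it is sound. The question is the input.

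**Step 2: set the rows against each other.**
- Composite and ATE: 1.17 / 2.50 = 0.47. The ATE row is consistent within itself (1,000 / 2.50 = 400, halved 200), so 2.50 is not a slip in one cell.
- Composite and PE: 1.17 − 1.09 = 0.08 per 1,000 PY is all that remains for every patient without PE, arterial events included.
- ATE and MACE: if ATE includes MI and stroke, as Section 9.3.2 says of arterial thrombosis, at least 2.50 − 1.41 = 1.09 per 1,000 PY of ATE would have to fall outside a MACE definition that contains both.
- Table 1: the code list for thromboembolic events includes I74 but no MI or stroke codes such as I21 or I63. It therefore does not match Section 9.3.2.

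**Step 3: consequence if ATE 2.50 is right.**

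| Composite rate | d, all | HR, all | d, subset | HR, subset |
|---|---|---|---|---|
| 2.50 (floor: every venous case is also an ATE case) | 19.3 | 3.58 | 12.8 | 4.79 |
| 1.17 + 2.50 = 3.67 (1.17 taken as VTE only, no overlap) | 28.4 | 2.86 | 18.8 | 3.64 |

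PYs per event would be at most 400 (200 at doubling) instead of 855 (427).

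**The case against.** The strongest reply is that ATE may be the faulty or differently defined row. It conflicts with two other rows, the composite and MACE. Under the narrower Table 1 code list, which omits MI and stroke, 1.17 could be close to right. This stands. It means the replacement figures are conditional, but it does not rescue the text: the table would still be wrong in its ATE row, and the code list would still disagree with Section 9.3.2.

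A reader might infer that 1.17 must be a VTE-only rate. It looks that way beside PE at 1.09, but the table strains this too. If 1.17 counts patients with DVT or PE, then 0.87 + 1.09 − 1.17 = 0.79 per 1,000 PY have both, about 91% of DVT patients (0.79 / 0.87). Relabelling the row on that guess could add a second error.

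Separate exclusion of prevalent cases, or age standardization, could move a composite rate somewhat, but would hardly explain a gap of more than two-fold.

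Three further inferences are tempting and not supported:
- That 10 expected events should read 9. The unrounded counts 8.73, 9.04 and 14.61 all rounded up give 9, 10 and 15 as printed, and the HR of 6.4 uses the unrounded count.
- That the decision to run the comparison turns on these expected events. Section 8.3 bases it on expected users and observed events, with the rule left to the SAP.
- That a normal observed rate would be read as a two- to three-fold excess over 1.17. No comparison of observed thromboembolic rates with Table 3 is planned; context comes from the concurrent treatment cohorts (Section 9.1).

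**Conclusion.** The point holds as an inconsistency. The thromboembolic, ATE and MACE rows of Table 3 cannot all be right under the protocol's endpoint definitions, and the 10 events and HRs of 6.4 and 9.9 are therefore unsupported for the endpoint as defined.

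The size is conditional. If ATE 2.50 is right, expected events are at least about 19 rather than 10 and the minimum HR is at most about 3.6 rather than 6.4, or about 28 events and 2.9 under the no-overlap reading. In the 5-year subset the floor gives about 13 events and HR about 4.8 rather than 9.9. These figures rest on 1:1 groups, no loss to follow-up, and the assumed two-sided 5% and 80% power. If the ATE row is at fault, the correction belongs there instead.

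This should be fixed but does not threaten the study. All eligible patients enter whatever these figures say, the primary objective is to estimate rates, and the HRs belong to an exploratory comparison for the final report if size permits. If 2.50 is right, the error is conservative. Section 9.5 itself warns that analysis is by data source and that no single source is likely to reach 835 ritlecitinib patients.

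**What to change.** - State in Table 3 footnotes what the thromboembolic, ATE and MACE rows each count.
- Reconcile those definitions with Section 9.3.2 (arterial thrombosis includes MI and stroke) and with the Table 1 code list (I74, no MI or stroke codes), so that endpoint text, codes and background rate describe one outcome.
- Give the composite rate for the endpoint as defined, from the data on file. If the ATE row proves wrong or differently defined, correct or relabel that row.
- Recompute PYs per event, expected events and both minimum HRs in Section 9.5, or size venous and arterial events separately. State the alpha and power used.

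The cost is a few table rows and footnotes, one code list check and one paragraph. The rates come from data the sponsor already holds, and neither design nor data collection changes.

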# 9.7.4. Subgroup Analyses

If study size permits, the following analyses will be conducted for the subgroups listed below: descriptive characteristics by exposure cohort, IRs by exposure cohort, and HRs for comparative analyses.

- Sex (male, female)
- Adolescent and adult populations, based on age on index date (12-17 years, 18 years and older)
- Prior systemic therapy
- To allow for sufficient follow-up for outcomes with long induction or latent periods, subgroup analyses will be conducted among the subset of patients with a minimum of 5 years of follow-up, defined as patients initiating the study treatments between 15 September 2023 and 14 September 2028.

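### Section 9.5 says the 5-year subset has lower minimum detectable HRs when its own figures are higher, and all six HRs come from event counts that assume no treatment effect

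*Protocol*

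**What the plan says.** Section 9.5 derives the ritlecitinib person-time as "3,864, assuming no lost to follow-up". It continues: "A 1:1 ratio of ritlecitinib:comparator patients would yield a total of 7,728 PYs and an expected number of events of 9, 10, and 15" for malignancy, thromboembolic events and serious infections. On that basis "there would be sufficient power to detect a minimum HR of 6.7, 6.4, and 4.3" for the same three endpoints.

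The next paragraph turns to patients with at least 5 years of follow-up: "Minimum detectable HRs will be lower for the subgroup analysis of patients with a minimum of 5 years of follow-up". The sentence after it says that 407 ritlecitinib patients, at 1:1 and with no loss, would give "sufficient power to detect minimum HRs of 10.3, 9.9, and 6.1".

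Section 9.7.4 explains why the subset exists: "subgroup analyses will be conducted among the subset of patients with a minimum of 5 years of follow-up", to allow for outcomes with long induction or latency. It makes no claim about power. The significance level, sidedness, power and formula behind the six HRs are not stated.

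**The concern.** There are two faults in the same two paragraphs.

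**Direction.** The text says the detectable HRs fall in the subset, and the next sentence prints larger ones for all three endpoints. Either the word or the numbers must be wrong.

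**Event counts.** The expected 9, 10 and 15 events are the person-years of both cohorts multiplied by one background rate. That is the count if ritlecitinib has no effect. A minimum detectable HR needs the count expected when that HR is true. With comparators at background, a true HR of 6.7 would produce far more than 9 malignancies, so 6.7 would not be the smallest detectable value.

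At stake is how the exploratory comparison in section 9.7.3 is read. Section 9.5 is the protocol's only quantitative statement of what that comparison can detect.

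**Working it through.** **Inputs.** Table 2 accrual and the section 9.5 follow-up multipliers; Table 3 rates of 1.13, 1.17 and 1.89 per 1,000 PY; 1:1 allocation. Assumed because unstated: two-sided 5% and 80% power, so z = 1.960 + 0.842 = 2.802.

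**Person-years per cohort.**
- Full: 74×8 + 96×7 + 110×6 + 127×5 + 144×4 + 161×3 + 123×2 = 3,864, matching the plan.
- 5-year subset (accrual years 1 to 5): 74×8 + 96×7 + 110×6 + 127×5 = 2,559, from 74 + 96 + 110 + 127 = 407 patients.

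**Reproducing the plan's HRs.** Log-rank (Schoenfeld) formula at 1:1: HR = exp(2 × 2.802 / √D), with D = 2 × PY per cohort × background rate.

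| | D | HR obtained | HR stated |
|---|---|---|---|
| Full, malignancy | 8.73 | 6.66 | 6.7 |
| Full, thromboembolic | 9.04 | 6.45 | 6.4 |
| Full, serious infection | 14.61 | 4.33 | 4.3 |
| Subset, malignancy | 5.78 | 10.28 | 10.3 |
| Subset, thromboembolic | 5.99 | 9.87 | 9.9 |
| Subset, serious infection | 9.67 | 6.06 | 6.1 |

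All six agree to within rounding. For full-cohort malignancy, one-sided 5% (5.4), 90% power (9.0) and Freedman's formula (37.5) do not. The numbers are therefore consistent with fewer events in the subset, and the word *lower* is what is wrong.

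**What the stated HRs imply.** Take comparators at 1.13 per 1,000 PY and HR 6.7. Comparator malignancies are 3,864 × 0.00113 = 4.37, ritlecitinib malignancies 6.7 × 4.37 = 29.3, total 33.6, not 9. To keep the total at 8.73, the comparator rate would have to be 8.73 / (3.864 × 7.7) = 0.29 per 1,000 PY, about a quarter of Table 3.

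**Recalculation.** Comparators at background, ritlecitinib at HR × background, so D = PY per cohort × rate × (1 + HR). Two methods at 80% power:
- Log-rank: solve ln(HR) × √D / 2 = 2.802.
- Exact: two-sided 5% conditional binomial test of the split between cohorts, averaged over a Poisson total with mean D.

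| | Stated | Log-rank | Exact | Exact power at stated HR | Exact power at log-rank HR |
|---|---|---|---|---|---|
| Full, malignancy | 6.7 | 3.5 | 4.1 | 99.4% | 65% |
| Full, thromboembolic | 6.4 | 3.5 | 4.0 | 99.2% | 65% |
| Full, serious infection | 4.3 | 2.9 | 3.2 | 97.5% | 68% |
| Subset, malignancy | 10.3 | 4.2 | 5.2 | 99.9% | 61% |
| Subset, thromboembolic | 9.9 | 4.2 | 5.1 | 99.9% | 61% |
| Subset, serious infection | 6.1 | 3.4 | 3.9 | 99.2% | 66% |

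The log-rank values fall well short of 80% exact power, so they are too optimistic at these counts.

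**Size of the subset's loss.** From unrounded values, the subset's minimum HR exceeds the full cohort's by 18% to 20% (log-rank: 4.23/3.53, 4.16/3.48, 3.38/2.87) or 22% to 26% (exact: 5.19/4.12, 5.08/4.05, 3.91/3.21).

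**The case against.** The case for leaving the text alone is that the correct, larger HRs follow the mistaken word at once, that the event-count error is in the cautious direction, and that nothing primary depends on either. The primary objective is rate estimation, and the comparison is exploratory and for the final report only. This stands as a limit on importance. It does not remove a contradiction within one paragraph or make the stated values minima.

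It is also fair that the recalculation rests on a choice. Table 3 gives rates for AA patients in Denmark, not for baricitinib initiators in three countries, and alpha and power are inferred. The stated HRs are overstated only if comparators have roughly the Table 3 rate. The plan offers no other rate.

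The recalculated values are a best case as well. Section 9.5 itself warns that analysis is by data source and that no single source is likely to reach 835 patients. It assumes no loss to follow-up. Censoring at discontinuation or switch (Figure 1, section 9.3.1) would cut person-time further where it is applied. All of these raise the achievable HR.

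Three stronger readings are tempting and not supported:
- *That the plan presents the subset as its more sensitive analysis.* This would rest on one wrong word; section 9.7.4 justifies the subset by latency alone.
- *That these HRs decide whether the comparison is run.* Section 8.3 bases that rule on expected users and observed events and leaves it to the SAP.
- *That the subset is about half as bad again.* The printed ratio 10.3/6.7 = 1.54 uses the figures shown above to be miscounted; the corrected gap is 18% to 26%.

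**Conclusion.** The point holds in two parts.

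The direction is wrong as written, and this needs no assumption: the subset's figures are higher for all three endpoints, as they must be for a nested subset with about two thirds of the person-time (2,559/3,864 = 0.66).

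The six HRs rest on event totals counted at HR = 1. If comparators have the Table 3 rate, and at two-sided 5% and 80% power, they overstate the minimum detectable HR by a factor of about 1.3 (4.3/3.2, full-cohort serious infection) to 2.0 (10.3/5.2, subset malignancy) against the exact test. The corrected values hold on the plan's own person-years with all sources combined; analysis by country and shorter exposure time will push them up.

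The consequence is limited to how the exploratory comparison is described and interpreted. The primary incidence rates and the accrual plan are untouched. It should be corrected, but it is not critical.

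**What to change.** In section 9.5:

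1. Replace *lower* with *higher* in the sentence on the 5-year subset, and add that the subset has less power than the full cohort.
2. Recompute the six minimum HRs with comparators at the background rate and ritlecitinib at HR times that rate. Use an exact method or give a range. On the current person-years the exact values are about 4.1, 4.0 and 3.2 (full cohort) and 5.2, 5.1 and 3.9 (subset). The log-rank values of 3.5, 3.5 and 2.9, and 4.2, 4.2 and 3.4, should not stand alone.
3. State alpha, sidedness, power, method and the assumed comparator rate. Label 9, 10 and 15 as events expected under no effect, and correct the 10: 7,728 × 0.00117 = 9.04, and the stated HR of 6.4 matches 9.04 events, whereas 10 would give 5.9.
4. Add that analysis by data source and censoring at discontinuation will raise these values.

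The cost is rewording two paragraphs and rerunning six numbers. No change to design, data or endpoints is needed.
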